#### 4.2.2 SECONDARY ENDPOINTS

Monthly, health related quality of life scores (HRQoL) will be obtained and the 36-Item Short Form Health Survey (SF-36). These instruments have been validated. For the secondary outcome measure, baseline HRQoL will be compared to the 30, 60, and 90 day HRQoL scores.

#### 4.2.3 EXPLORATORY ENDPOINTS

NA

## 5 STUDY ENROLLMENT AND WITHDRAWAL

### 5.1 PARTICIPANT INCLUSION CRITERIA

1. The diagnosis of PSACH is based on clinical assessment either in person or by photographic review by skeletal dysplasia specialist ([name]),
2. Healthy beyond PSACH associated complications,
3. Age at enrollment between 18 years to 70 years.
4. Baseline pain level of 2 or higher on 10 point scale.

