### 4.2.1 PRIMARY ENDPOINT

Self-reported pain will be obtained from all study subjects using the Numeric Pain Rating Scale to score the subject's pain on a 0 to 10 scale. This scale has been validated and widely used. A pain level will be assessed with enrollment in order to assure the participant has pain. An additional assessment will take place at the first visit (day 0). Pain will then be ascertained daily (including during the "washout" period between the two intervention periods) through a daily pain log kept by participants. The pain logs will be requested from participants at each follow-up visit and at the end of each month in the treatment periods, and data from the pain logs will be compiled and analyzed

at the start and end of each of the two treatment periods (on days 0, 90, 120, and 210). Monthly pain averages will be compared to baseline.

The primary endpoint will be change in pain score between baseline and monthly average pain scores. The pain score on each day of month one will be averaged to obtain the average pain score for month one, and the same will be done for months two and three, and each of the monthly average scores for resveratrol and placebo periods will be compared to baseline.

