## 10 STATISTICAL CONSIDERATIONS

## 10.1 STATISTICAL AND ANALYTICAL PLANS

The primary outcome (change in pain between baseline and monthly pain average score) will be scored using the the Numeric Pain Rating Scale. Based on prior studies that utilized these scales, a difference of at least 2 units on the 11-point scale are considered to be a reflection of a true change in pain. Median and mean monthly pain will be compared. The pain score on each day of month one will be averaged to obtain the average pain score for month one, and the same will be done for months two and three, and each of the monthly average scores will be compared to baseline. For the secondary outcome measure, baseline HRQoL will be compared to the 30, 60, and 90 day HRQoL scores.

Data from the daily pain logs and the monthly HRQoL assessments will be used to evaluate changes in outcomes within each intervention period stratified by study drug. The analysis will be performed within the framework of the 2x2 crossover study design. Baseline characteristics (demographic and clinical) will be tabulated. Exploratory analyses will be performed to assess differences in outcomes as stated above after further stratification by gender.

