## 10.2 STATISTICAL HYPOTHESES

The primary hypothesis is that patients' report of pain (and/or use of pain medication) will be 2.8 points lower on the pain scale (0-10) while on the resveratrol than while on placebo.

The secondary hypothesis for this study states that the change in self-reported HRQoL from the start of the study period to the end will be different in PSACH patients during the period they are on resveratrol compared to when they are on placebo.

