### 10.5 SAMPLE SIZE

Although studies haven't quantified pain variability in PSACH, other studies have utilized a pain VAS and have reported standard deviation (SD) of the difference between scores for the same patient of about 10-15 on a 1-100 scale. In addition, previous research by one of the investigators has suggested that a strong placebo effect can be present in studies using the pain VAS at a magnitude of about 20 on a 1-100 scale. Assuming a similar degree of variability in our study population and considering the placebo effect as reported, with a sample size of 30 participants at a Type I error rate of 5%, the minimal detectable difference would be 2.8 units at a SD of 10 and power of 80%, 4.25 at a SD of 15 and power of 80%, 3.3 at a SD of 10 and power of 90%, and 4.9 at a SD of 15 and power of 90%. Considering that there are about 300 potential patients that can be approached through the "Little People of America" support group and the Facebook PSACH group, we should be able to recruit into the study at least half of those highly motivated and invested individuals. We should be able to achieve our sample size of 30 patients for this study, even assuming a considerably high 33% attrition rate. We will screen 60 to enroll 30.

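### The 2.8-point primary hypothesis in Section 10.2 appears to be an unscaled 1-100 figure from Section 10.5; it fits neither N=30 nor the entry threshold of 2

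*Combined protocol and SAP*

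**What the plan says.** Section 4.2.1 records the primary endpoint "using the Numeric Pain Rating Scale to score the subject's pain on a 0 to 10 scale". Criterion 4 of Section 5.1 sets the entry level: "Baseline pain level of 2 or higher on 10 point scale". Section 10.2 states the primary hypothesis, that reported pain "will be 2.8 points lower on the pain scale (0-10) while on the resveratrol than while on placebo".

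Section 10.5 works on a different scale. It takes from other studies a "standard deviation (SD) of the difference between scores for the same patient of about 10-15 on a 1-100 scale" and adds that "a strong placebo effect can be present in studies using the pain VAS at a magnitude of about 20 on a 1-100 scale". For 30 participants and a 5% Type I error rate, it concludes that "the minimal detectable difference would be 2.8 units at a SD of 10 and power of 80" per cent. It also gives 4.25 (SD 15, 80%), 3.3 (SD 10, 90%) and 4.9 (SD 15, 90%).

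Section 10.1 supplies a third benchmark: "a difference of at least 2 units on the 11-point scale are considered to be a reflection of a true change in pain". Sections 4.1 and 10.5 give an enrolment of 30; Section 10.6.1 gives one hundred. Nothing in the document links the entry threshold to the hypothesised difference or to the placebo response.

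**The concern.** The same number, 2.8, stands in Section 10.5 as units on a 1-100 scale and in Section 10.2 as points on 0-10, a tenfold difference. If it was carried over without rescaling, the primary hypothesis states an effect that nobody derived. If 2.8 points was truly meant, nothing supports it: it exceeds the 2-unit change in Section 10.1 and has no link to the calculation in Section 10.5.

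Taken literally, it also collides with the floor of the scale. Someone who enters at 2 cannot fall by 2.8, and the plan itself allows for a placebo response of about 2 points. At stake are whether the stated hypothesis is attainable in the population enrolled, and whether the sample size rationale describes the trial being run.

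**Working it through.** **Inputs.** N=30, alpha 5%, SD of the within-patient difference 10-15, placebo response about 20 on 1-100 (Section 10.5); N=100 (Section 10.6.1); entry at 2 or more (Section 5.1); floor at 0 (Section 4.2.1); 2.8 points (Section 10.2). Conversion from 1-100 to 0-10 is taken as division by 10. Sidedness is not stated, so two-sided is used first.

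**Step 1: the plan's own figures.** For a within-patient comparison, detectable difference = (z for alpha + z for power) × SD / √N. At SD 10 and 80% power with N=30: (1.960 + 0.842) × 10 / √30 = 5.11, or 5.29 with the noncentral t. The stated 2.8 is not reproduced. A one-sided test gives 4.54 (z) or 4.65 (t), which does not rescue it.

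| SD, power | Stated | N=30 (two-sided t) | N=100 (two-sided t) | N implied (z) |
|---|---|---|---|---|
| 10, 80% | 2.8 | 5.29 | 2.83 | 100.1 |
| 15, 80% | 4.25 | 7.94 | 4.24 | 97.8 |
| 10, 90% | 3.3 | 6.12 | 3.27 | 96.5 |
| 15, 90% | 4.9 | 9.19 | 4.91 | 98.5 |

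All four values fit N of about 100. With N=30 and SD 10, power at 2.8 units is about 32%.

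**Step 2: on the endpoint's scale.** 2.8 / 10 = 0.28 points. SD 10-15 becomes 1.0-1.5, so at N=30 and 80% power the detectable difference is 0.53-0.79 points.

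**Step 3: the floor, taking 2.8 points literally.** Placebo response 20 / 10 = 2 points. Minimum baseline for the full difference: 2 + 2.8 = 4.8. Visible difference = min(2.8, max(0, baseline − 2)): 0 at baseline 2, 1 at 3, 2 at 4, and 2.8 from 5 upward. With no placebo response, an entrant at 2 can still show at most 2.0.

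The document gives no baseline distribution. Assuming integer baselines spread evenly:
- over 2-10: (0 + 1 + 2 + 6 × 2.8) / 9 = 2.20
- over 2-7: (0 + 1 + 2 + 3 × 2.8) / 6 = 1.90
- over 2-6: (0 + 1 + 2 + 2 × 2.8) / 5 = 1.72

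With a 1-point placebo response the means are 2.51, 2.37 and 2.28.

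**Step 4: what the floor does to power at N=30.**
- *Large effect.* In the 2-6 case the visible effects have SD √(20.68/5 − 1.72²) = 1.09. Combined with SD 1.5, the total is √(1.09² + 1.5²) = 1.85. Noncentrality is 1.72 × √30 / 1.85 = 5.1, so power exceeds 99%. If half the sample showed nothing and half the full 2.8, power would still be about 95-99%.
- *Modest effect.* For a true effect of 0.53 (SD 1.0) or 0.79 (SD 1.5), a quarter of participants showing no effect cuts power from about 80% to about 53%. The quarter is an assumption. After a 2-point placebo response an entrant at 3 still has 1 point of room, so only entrants near 2 lose an effect of this size. An even spread over 2-6 puts one in five at 2.

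**The case against.** The strongest reply is that the floor argument leans on a number that is probably a slip. If 0.28 points was meant, the baseline needed is 2 + 0.28 = 2.28 and the clash with criterion 4 nearly disappears. This stands: the root defect is the scale and sample size mismatch, and the entry threshold is secondary.

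A reader might infer that admitting pain of 2 dooms the trial, or that a negative result could not be told apart from a floor effect. The documents do not support either:
- The 2.8 is a hypothesised mean, not a bar for success, and Section 10.4.1 analyses a mixed model that takes account of baseline, treatment and sequence.
- The diluted means in Step 3 (1.72-2.51) are far above the detectable 0.53-0.79.
- Daily logs in both periods would show zero scores on placebo, and Section 10.4.2 foresees a zero-inflated model if more than 30% report no pain. That model creates no room for improvement, but it shows that zeros were considered.

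The word cannot also needs its limits. Section 10.5 says only that a placebo effect can be present, and a monthly average may exceed the day 0 score. Section 10.2 mentions use of pain medication as well, which the pain floor does not cap, though it is not part of the primary endpoint in Section 4.2.1.

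Finally, a higher entry threshold would cost participants in a rare disease. That is a trade-off for the sponsor, and the case for imposing it is not made here.

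**Conclusion.** Section 10.2 is wrong as written. Its 2.8 points on 0-10 appears to be the 2.8 units of Section 10.5 without rescaling. This is an inference from the matching number; the document does not say so. Section 10.5 is in turn inconsistent with N=30: the detectable difference at 80% power is about 5.3-7.9 units (0.53-0.79 points), nearly twice what is stated, and the stated values fit the one hundred of Section 10.6.1. These results rest on a within-patient comparison, a two-sided 5% test and the plan's own SDs.

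On the plan's own placebo assumption, entrants below 4.8 cannot show the full 2.8 points, so any share of them pulls the mean below it unless others exceed 2.8. How far depends on a baseline distribution that is not given. The harm is to the attainability of the stated hypothesis, and to power mainly when the true effect is modest. It does not follow that the trial must fail or that criterion 4 must change.

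**What to change.** 1. Reconcile Sections 10.2, 10.5 and 10.6.1 on one scale (0-10) and one sample size.
2. Recompute the detectable differences in Section 10.5 for the number actually enrolled, stating the sidedness. At N=30 and 80% power they are about 0.53-0.79 points; with the 10% loss mentioned in Section 10.6.1 (27 participants), about 0.56-0.84.
3. Restate the hypothesis in Section 10.2 on 0-10 as a difference consistent with the recomputed figures and with the 2-unit change in Section 10.1, and drop 2.8. Do not substitute 0.28: N=30 detects it with only about 32% power at SD 1.0.
4. Repeat the floor check for the chosen figure. If it is 2 points, for example, the baseline needed after a 2-point placebo response is 2 + 2 = 4, and the text should say so.
5. Keep the entry threshold, and state that the trial does not test a 2.8-point difference because low-baseline entrants cannot show it.

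The cost is one or two sentences and less favourable stated detectable differences. Eligibility, procedures and recruitment are unaffected.

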### 5.2 PARTICIPANT EXCLUSION CRITERIA

1. Current use of resveratrol
2. Current use of blood thinners, lovastatin, ketoconazole, itraconazole, fexofenadine and triazolam.
3. Other non-PSACH related health conditions, e.g. cancers.
4. Pregnancy or breastfeeding.
5. Women of childbearing age not using adequate contraception methods known to prevent pregnancy during the study.
6. Participation in another clinical study and/or using investigational agents.
7. Use of NSAIDs or aspirin.
8. Current use of Alfentanil, Cyclosporine, Dihydroergotamine, Dofetilide, Ergotamine, Fentanyl, Flibanserin, Oxycodone, Pimavanserin, Pimozide, Quinidine, Saquinavir, Sirolimus, Tacrolimus, Temsirolimus, Theophylline, Tizanidine, Thioridazine, Fosphenytoin, Phenytoin or Warfarin.
9. Age 17 years or less.
10. Platelet count below 50,000 per  $\mu\text{l}$  on baseline CBC.

### 5.3 STRATEGIES FOR RECRUITMENT AND RETENTION

Recruitment will be conducted at Little People of America convention (n=300 PSACH members) and the PSACH blog (Facebook page: "Pseudoachondroplasia Dwarfish – and growing!!!" Closed group with 211 members). We will be recruiting International participants that contact us with interest in the study or that international colleagues refer to us. This recruitment strategy reaches out to the most active population in order to recruit motivated participants

that will complete the 7 month study. Monthly calls to participants to assess compliance and record keeping as well as any adverse events will be done to increase retention.

## 5.4 PARTICIPANT WITHDRAWAL OR TERMINATION

### 5.4.1 REASONS FOR WITHDRAWAL OR TERMINATION

Participants are free to withdraw from the study at any time upon notification to the PI or study coordinator via phone or written request via email or postal mail An investigator may terminate participation in the study if:

- a. Any clinical adverse event (AE) or other medical condition or situation occurs such that continued participation in the study would not be in the best interest of the participant.
- b. The participant meets an exclusion criterion (either newly developed or not previously recognized) that precludes further study participation.

### 5.4.2 HANDLING OF PARTICIPANT WITHDRAWALS OR TERMINATION

Participants who choose to withdraw or are withdrawn due to an AE or exclusion criteria must return the unused portion of study materials to the study coordinator. **All mailing/communication costs will be paid by the study.**

All participants withdrawn/discontinued will be followed for 1 month to make sure that no AEs have developed after withdrawal from the study. If a participant was withdrawn due to AEs, they will be advised to seek medical help with their primary care physician. Those costs are not covered by this study.

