## 5.5 PREMATURE TERMINATION OR SUSPENSION OF STUDY

This study may be temporarily suspended or prematurely terminated if there is sufficient reasonable cause. Written notification, documenting the reason for study suspension or termination, will be provided by the study PI to IND sponsor. If the study is prematurely terminated or suspended, the PI will promptly inform the IRB and will provide the reason(s) for the termination or suspension

Circumstances that may warrant termination or suspension include, but are not limited to:

- Determination of unexpected, significant, or unacceptable risk to participants;
- Demonstration of efficacy that would warrant stopping;
- Insufficient compliance to protocol requirements;
- Data that are not sufficiently complete and/or evaluable;
- Determination of futility.

A suspended study may resume once concerns about safety, protocol compliance, data quality are addressed and satisfy the IRB and/or FDA

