#### **Follow-up Visit (Visit 4, Day 90 +/- 5 working days)**

- Inform patient that they are supposed to not take any study medication for the next 30 days but should continue their pain logs.
- Record adverse events as reported by participant to study co-ordinator. Study coordinator will ask about gastrointestinal health, any bleeding events and unusual bruising. PI will follow up with participant to assess the adverse events and determine whether to terminate participation.
- Record participant's adherence to treatment protocol.
- Inquire about any medication and health condition changes.
- Administer HRQoL instrument.
- Request participant to mail back or email their pain log and mail back any unused medication or email a photo of the empty bottle. The data from the pain logs will be compiled and analyzed at the start and end of each two treatment periods (on days 0, 90, 120, and 210).
- Ask participants about which medication, resveratrol or placebo, they think they were taking during the last 90 day period (evaluation of the success of blinding).
- Female participants in the United States will be asked to take a urine pregnancy test at local labcorp or local lab. Email a photo of self administered pregnancy test supplied by us for female international participants within 30 days prior to next medication mail out.
- Participants will be asked to complete blood draw to the closest LabCorp or from their local facility at our cost. For the International participants complete blood draw to the closest local facility blood and mailed to us for analysis at local Labcorp lab.
- The complete metabolic panel includes analysis of renal function [blood urea nitrogen (BUN), creatinine], liver function [total bilirubin, alanine aminotransferase (ALT), alkaline phosphatase (ALP), and aspartate aminotransferase (AST)], glucose, electrolytes [calcium, sodium, potassium, carbon dioxide (bicarbonate), chloride], protein [albumin, total protein]. The complete blood count (CBC) includes analysis of red blood count, hemoglobin, hematocrit, white blood cell count, platelet count. Platelet count below 50,000 per  $\mu$ l in CBC which indicates increased bleeding risk will result in removal from the study.

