7.3.4 FINAL STUDY VISIT

**Final Study Visit (Visit 8, Day 210 +/- 5 working days)**

- Inform patient that they have completed the study.
- Record adverse events as reported by participant to study co-ordinator. Study coordinator will ask about gastrointestinal health, any bleeding events and unusual bruising. PI will follow up with participant to assess the adverse events and determine whether to terminate participation.
- Record participant’s adherence to treatment protocol.
- Inquire about any medication and health condition changes.
- Participants will be asked to complete blood draw from their local facility at our cost to assess kidney function, liver function and blood cell count. The complete metabolic panel includes analysis of renal function [blood urea nitrogen (BUN), creatinine], liver function [total bilirubin, alanine aminotransferase (ALT), alkaline phosphatase (ALP), and aspartate aminotransferase (AST)], glucose, electrolytes [calcium, sodium, potassium, carbon dioxide (bicarbonate), chloride], protein [albumin, total protein]. The complete blood count (CBC) includes analysis of red blood count, hemoglobin, hematocrit, white blood cell count, platelet count. Platelet count below 50,000 per µl in CBC which indicates increased bleeding risk will result in removal from the study.
- Administer HRQoL instrument.
- Request participant to mail back or email their pain log and mail back any unused medication or email a photo of the empty bottle. The data from the pain logs will be compiled and analyzed at the start and end of the two treatment periods (on days 0, 90, 120, and 210).
- Ask participants about which medication, resveratrol or placebo, they think they were taking during the last 90 day period (evaluation of the success of blinding).

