7.3.5 EARLY TERMINATION VISIT

If the study terminates early, the participants will be called and notified of study termination. In addition, the call will include the following:

- Information will be collected on any adverse events that the subjects may have experienced during their participation in the study. If the participant reports any adverse events, especially if they were the reason for early termination, the participant will be advised to seek medical assistance from their primary care physician.
- Participants will be asked to mail back any unused medication or email a photo of the empty bottle. Participants will be asked to mail back or email their pain log.
- HRQoL will be administered.
- Participants will be informed that they will be re-contacted 30 days post-termination visit to assess any AE/SAE.

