## 8.3 TIME PERIOD AND FREQUENCY FOR EVENT ASSESSMENT AND FOLLOW-UP

The occurrence of an AE or SAE may come to the attention of study personnel during study phone interviews with the study participants or upon review by the DSMB. All AEs including local and systemic reactions not meeting the criteria for SAEs will be captured on the appropriate case report forms. Information to be collected includes event description, time of onset, clinician's assessment of severity, relationship to study drug (assessed only by those with the training and authority to make a diagnosis), and time of resolution/stabilization of the event. All AEs occurring while on study will be documented appropriately in the database regardless of relationship. All AEs will be followed to adequate resolution.

Any PSACH-related medical issue present at the time the participant is screened will be considered as baseline and not reported as an AE. However, if the study participant's condition deteriorates at any time during the study, it will be recorded as an AE. Unanticipated problems will be recorded in the data collection system throughout the study. Changes in the severity of an AE will be documented to allow an assessment of the duration of the event at each level of severity to be performed. AEs characterized as intermittent require documentation of onset and duration of each episode.

The study staff will record all reportable events with start dates occurring any time after informed consent is obtained until 7 (for non-serious AEs) or 30 days (for SAEs) after the last day of study participation. At each study visit, the study staff will inquire about the occurrence of AE/SAEs since the last visit. Events will be followed for outcome information until resolution or stabilization.

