### 8.5 STUDY HALTING RULES

Administration of study agent will be halted study-wide when any of the following occur and are reported to the DSMB:

- three grade 3 AEs
- three grade 1 or grade 2 AEs of the same type
- three grade 1 or grade 2 AEs related to liver function
- one grade 4 or 5 AE

The research coordinator will notify the principal investigators and co-investigator immediately when the the study stopping criteria are met and enrollment screens will stop accepting new study participants. The principal investigator will inform the Data and Safety Monitoring Board (DSMB) members within 24 hours of this occurrence and will provide the DSMB with AE listing reports. The DSMB will convene an ad hoc meeting by teleconference or in writing as soon as possible. The DSMB will provide recommendations for proceeding with the study to the principal investigator. The principal investigator will inform the FDA of the temporary halt and the disposition of the study.

An individual participant will be asked to discontinue study medication if any of the following occur:

- one grade 3, 4, or 5 AE
- three grade 2 AEs
- five grade 1 AEs

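### A participant who withdraws during a resveratrol period, or is in one when the study is terminated early, has no required metabolic panel or CBC after exposure.

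*Combined protocol and SAP*

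**What the plan says.** Blood is drawn at three points. The first is baseline (7.3.2; screening column in 7.3.7), before any study product. The second follows period 1. The Visit 4 text (Day 90) says "Participants will be asked to complete blood draw to the closest LabCorp or from their local facility at our cost", while 7.3.7 puts this draw in the washout column. The third is Day 210 (7.3.4), where participants are asked to "complete blood draw from their local facility at our cost to assess kidney function, liver function and blood cell count". The other follow-up calls and the Day 240 contact involve questions only.

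Two sections deal with early exit:

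- **5.4.2, individual withdrawal.** Unused product is returned, and "All participants withdrawn/discontinued will be followed for 1 month to make sure that no AEs have developed after withdrawal from the study". A participant withdrawn for an adverse event is also advised to see their own physician, and the study does not pay for that care.
- **7.3.5, early termination visit.** Its opening is about the study as a whole: "If the study terminates early, the participants will be called and notified of study termination". The call covers adverse events, product return or a bottle photo, the pain log and HRQoL. Participants are told that "they will be re-contacted 30 days post-termination visit to assess any AE/SAE".

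Neither section lists a blood draw. Section 8.2.1 grades creatinine, potassium, ALT, AST, alkaline phosphatase, bilirubin, platelets and hemoglobin. The study-wide halting rules in 8.5 include "three grade 1 or grade 2 AEs related to liver function".

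**The concern.** The protocol treats laboratory values as safety outcomes and lets them count toward a halt, but it does not obtain them from the people who leave while taking the active product. The calls ask about gastrointestinal health, bleeding and bruising. They cannot reveal a raised ALT, creatinine or potassium in someone who feels well, and grade 1 ALT begins just above the upper limit of normal.

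Leavers may also not be a random subset for safety, because an adverse event is one of the reasons for termination in 5.4.1. The gap is most awkward if the whole study is stopped. Section 5.5 gives "Determination of unexpected, significant, or unacceptable risk to participants" as a possible reason, and even then 7.3.5 has people questioned and not tested.

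**Working it through.** The plan states no figure on this point, so there is none to reproduce. The check has two parts: who is left without a panel, and roughly how many people that could be.

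**Who is affected**

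| Sequence | Exit time | Last required panel | Panel after resveratrol? |
|---|---|---|---|
| Resveratrol first | Days 0–90, before the post-period-1 draw | Baseline | No |
| Resveratrol first | Days 120–210 (on placebo) | Day 90 or washout | Yes |
| Placebo first | Days 0–90 (on placebo) | Baseline | Not exposed |
| Placebo first | Days 120–210, before the final draw | Day 90 or washout, after placebo only | No |

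Each period lasts 90 days (6.1.9), so the longest unchecked exposure is about 89 days in either sequence. Washout exits are left out. A resveratrol-first participant who leaves in washout before the draw would add slightly to the count if the timing in 7.3.7 is followed.

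**How many, as an illustration**

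Inputs from the documents:
- 30 enrolled (4.1 and 10.5). Section 10.6.1 says one hundred, which conflicts; 30 is used here.
- Loss of 10%, the power allowance in 10.6.1.
- Attrition of 33%, mentioned in 10.5, where it may be a recruitment allowance.

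Assumptions, because the documents do not give these: equal sequences, and dropout time uniform over 210 days.

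Share of dropouts on resveratrol with no later panel = 0.5 × (90/210) + 0.5 × (90/210) = 0.429.

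- 10% loss: 30 × 0.10 = 3 dropouts, and 3 × 0.429 = 1.29, about 1.3. Over all possible timings the range is 0 to 3.
- 33% attrition: 30 × 0.33 = 9.9, taken as 10, and 10 × 0.429 = 4.29, about 4.3. The range is 0 to 10.

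**Early stop of the whole study**

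If entries are even over the 5-year study, the mean number active is 30 × 210 / (5 × 365) = 3.45, and 3.45 × 0.429 = 1.5 would be in a resveratrol period. If all 30 entered together, the number is 0 (during washout) to 15 (during either treatment period).

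**Effect on what the laboratory data can exclude**

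With zero events in n people who have a panel after resveratrol, the one-sided 95% upper bound on the event rate is 1 − 0.05^(1/n). It is 9.5% at n = 30. If every dropout left on resveratrol, it becomes 10.5% at n = 27 (10% loss) and 13.9% at n = 20 (33% attrition).

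**Is the gap closed elsewhere?**

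Section 8.3 follows events to resolution, but only once an event is known. An ad hoc test is not forbidden, but no section requires one.

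**The case against.** The strongest reply is that sparse laboratory monitoring is a deliberate choice for an over-the-counter product at a low dose. Nobody has a panel at Days 30, 60, 150 or 180, so the missing exit draw contradicts nothing in the plan. The dose of 125 mg/day is 2000/125 = 16 times lower than the 2 g/day reached in the cited 52-week trial, and the renal failure listed in 2.3.1 occurred with a micronized formulation given together with a cancer drug. The investigator follows up reported events. If a halting rule is met, the DSMB convenes and can ask for tests. All of this stands. It makes the expected harm small and limits the gap to symptom-free changes, but it does not supply a required test.

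A reader might infer more than the documents support in three ways:

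- **That one missed liver case seriously weakens the halting rule.** One event is a third of any count-to-three rule, which says nothing about how likely a missed case is. The documents give no laboratory event rate at this dose. The rule is also not arm-specific, and 8.5 separately halts on three grade 1 or 2 events of the same type.
- **That people who only stop medication under 8.5 also lose their panel.** Section 8.5 asks them to stop the product and does not take them off the visit schedule. The pairing of withdrawn with discontinued in 5.4.2 leaves some room for doubt, but it is not enough to claim a gap for them.
- **That the plan predicts 3 or 10 dropouts.** The 10% is an allowance for power, and the 33% may concern recruitment.

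**Conclusion.** The omission is clear from the text. Anyone who withdraws during a resveratrol period, or is in one at an early study stop, has no protocol-required metabolic panel or CBC after exposure. Confidence in that is high.

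Confidence in the size is much lower. The estimates of 1.3 and 4.3 people rest on 30 enrolled, equal sequences, uniform dropout timing and two percentages that were not offered as dropout forecasts. The ranges of 0 to 3 and 0 to 10 are the safer statement.

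The consequence is confined to safety ascertainment. The primary and secondary efficacy analyses are untouched, and nothing here suggests that participants face a substantial laboratory risk. This is a cheap improvement that the sponsor should consider.

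**What to change.** Bring the next scheduled panel (Day 90 or Day 210) forward to early exit, at study cost and through the same facilities. Three edits do this:

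1. **5.4.2:** require the panel for anyone who withdraws or is withdrawn.
2. **7.3.5:** add the panel, and state that the visit applies to individual withdrawal as well as to termination of the study.
3. **7.3.7:** add an early-termination column that shows it.

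Set a target of about 7 days after the last dose. Section 4.1 suggests that carry-over may last up to two weeks, so a draw in week 4 could miss a transient change or pick up an unrelated one. The target also fits 8.3, which records events "until 7 (for non-serious AEs) or 30 days (for SAEs) after the last day of study participation". Accept a later draw up to the end of the one-month follow-up, and record the days since the last dose so that the result can be weighed. Grade results under 8.2.1 and report them to the DSMB for use under 8.5. No change to 8.5 is needed for participants who only stop medication.

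The cost is small, because an early leaver uses a draw that was already planned. The added work is mainly logistics for international samples, which are drawn locally and mailed. Some leavers will decline, so the gap would narrow without closing fully.
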